3.8 Adverse events

3.8.1 Adverse event management

Adverse events (AE) are defined as *any untoward medical occurrence in a clinical trial patient and which do not necessarily have a causal relationship with the treatment*. All AEs will be listed on the appropriate Case Report Form for routine return to the 'FASHIoN' central office.

Serious adverse events (SAE) are defined as any *untoward and unexpected medical occurrence that:*

1. *Results in death,*
2. *Is life-threatening*

3. *Requires hospitalisation or prolongation of existing inpatients' hospitalisation,*
4. *Results in persistent or significant disability or incapacity,*
5. *Is a congenital anomaly or birth defect*
6. *Any other important medical condition which, although not included in the above, may require medical or surgical intervention to prevent one of the outcomes listed.*

All SAEs will be entered onto the reporting form and faxed to dedicated fax at WMSCTU within 24 hours of the investigator becoming aware of them. Once received, causality and expectedness will be confirmed by the CI. SAEs that are deemed to be unexpected and related to the trial will be notified to the Research Ethics Committee (REC) within 15 days. All such events will be reported to the Trial Steering Committee and Data Monitoring Committee at their next meetings. SAEs that may be expected as part of the surgical interventions, and that do not need to be reported to the main REC are: complications of anaesthesia or surgery (wound infection, bleeding or damage to adjacent structures such as nerves, tendons and blood vessels, delayed wound healing, and thromboembolic events, hip fracture, osteonecrosis and traction related neuropathies). SAEs that may be expected as part of the conservative care interventions and that do not need to be reported to the main REC are: transient increase in pain, delayed onset muscle soreness or mild bleeding at injection or acupuncture needle sites. All participants experiencing SAEs will be followed-up as per protocol until the end of the trial.

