3.8.2 Risks and benefits

Both interventions are thought to provide benefit in patients with FAI. There is thought to be a longterm risk of osteoarthritis in patients with FAI. It is not known whether conservative care or arthroscopic surgery have an effect on this risk. The short-term risks of this study relate to the two interventions. These risks are described below:

Operative

Hip arthroscopy requires a general anaesthetic. The risk of complications from hip arthroscopy is about 1-2%⁶⁰. These include:

- Infection – thought to be less than 1 in 1000. If the infection occurred deep within the joint it may require more procedures to wash out the hip joint.
- Bleeding – possibly causing bruising or a local haematoma.
- Traction related – to allow the small arthroscopy instruments into the hip joint, traction is required to separate the hip joint surfaces. Sometimes after the procedure the pressure from the traction can cause some numbness in the groin, leg or foot. The numbness usually resolves within a few hours or days.
- Osteonecrosis – during surgery the blood supply to the hip joint could be damaged. However, there are no reported cases of osteonecrosis following arthroscopic hip impingement surgery so this is a very small risk.
- Femoral neck fractures - This is also a very rare complication. This complication would require a further procedure to fix the fracture.

Non-operative

There are some small risks with pain medications and joint injection. However, the main risk is muscle soreness and transient increases in pain from the exercises that will be undertaken.

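### The SAE definition in Protocol 3.8.1 includes the word *unexpected*, which contradicts the section's own reporting steps and could take serious listed complications out of the 24-hour report

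*Protocol*

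**What the plan says.** Protocol section 3.8.1 sets out the following chain.

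- **Definition.** An SAE is any "untoward and unexpected medical occurrence that" meets one of six seriousness criteria, from death to an important condition needing intervention.
- **Site duty.** All SAEs go on the reporting form and are faxed to the trials unit within 24 hours of the investigator learning of them.
- **CI's judgement.** "Once received, causality and expectedness will be confirmed by the CI".
- **REC.** "SAEs that are deemed to be unexpected and related to the trial will be notified to the Research Ethics Committee (REC) within 15 days".
- **TSC and DMC.** The next sentence reads "All such events will be reported to the Trial Steering Committee and Data Monitoring Committee at their next meetings".
- **Expected events.** A list is introduced by "SAEs that may be expected as part of the surgical interventions, and that do not need to be reported to the main REC are". Its entries include "thromboembolic events, hip fracture, osteonecrosis and traction related neuropathies". A second list, for conservative care, covers temporary pain, muscle soreness and mild needle-site bleeding.

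Section 3.8.2 says of one surgical entry that "there are no reported cases of osteonecrosis following arthroscopic hip impingement surgery so this is a very small risk".

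Other parts of the protocol also capture harms. All adverse events go on case report forms (section 3.8.1). Complications are recorded at 6 weeks and at 3, 6 and 12 months (Table 2, section 3.5). The DMC's role includes safety (section 5.1).

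**The concern.** Seriousness and expectedness answer different questions. Seriousness decides whether an event is an SAE and must be reported quickly. Expectedness decides whether a reported SAE also goes to the REC. Section 3.8.1 puts the second test inside the first.

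The consequence falls at the site. An investigator who applies the definition to a listed complication that required admission or a further operation could conclude that it is not an SAE, because the protocol itself lists it as expected. The event would then travel on a routine form with no 24-hour report, and the site would have made the judgement that the protocol gives to the CI. What is at stake is the event's classification, its prompt reporting and its assured review as an SAE by the two oversight committees. The record of the event itself is not at stake.

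**Working it through.** The protocol states no figure on this point, so the check sets the sentences of sections 3.8.1 and 3.8.2 against one another.

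**Step 1: definition against later steps.** If every SAE is unexpected by definition, then:

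- the CI's confirmation of expectedness after receipt can only overrule a decision that the site has already made;
- the word *unexpected* in the REC rule filters nothing;
- both lists of expected SAEs are empty.

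Each of these provisions makes sense only if expected events can be SAEs. The definition is the sentence that does not fit.

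**Step 2: route to the TSC and DMC.** The phrase that opens the committee sentence has two possible antecedents: the unexpected and related SAEs of the sentence just before it, or all SAEs. Combined with the two readings of the definition, the question is whether an expected serious complication reaches the committees by this route.

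| | Committee sentence means unexpected and related SAEs | Committee sentence means all SAEs |
|---|---|---|
| Definition as written | No | No |
| Definition without *and unexpected* | No | Yes |

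The route is assured in one cell of four, so correcting the definition alone is not enough. The committee sentence must be settled too.

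**Step 3: osteonecrosis.** Section 3.8.1 lists it among expected surgical SAEs that need not go to the REC. Section 3.8.2 says that "there are no reported cases of osteonecrosis following arthroscopic hip impingement surgery". On the protocol's own account, a case in this pilot would be the first reported, and it would be exempt from REC notification.

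**Step 4: scale.** Inputs: 60 patients approached and a 30% planning rate (section 3.5, Sample size), 1:1 allocation (section 3.5, Treatment allocation), and a complication risk of about 1–2% (section 3.8.2).

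- Operations: 60 × 0.30 / 2 = 9.
- Expected complications: 9 × 0.01 = 0.09 to 9 × 0.02 = 0.18.
- Chance of at least one: 1 − 0.99^9 = 8.6% to 1 − 0.98^9 = 16.6%.
- Upper bound if all 60 were randomised, giving 30 operations: 1 − 0.99^30 = 26% to 1 − 0.98^30 = 45%.

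These figures cover complications of any severity. The chance of one that meets a seriousness criterion is lower, and the protocol gives no rate for it.

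**The case against.** The strongest reply is that the intended procedure can be recovered from the text. The listed complications are themselves called SAEs, the only exemption stated is from the main REC, and expectedness is judged once the form has arrived. A sensible site would therefore send the form. This is a fair account of the intent, but it requires the reader to set the definition aside, so the contradiction stands.

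Several stronger readings are tempting, and the documents do not support them.

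- **A reader might infer that serious surgical complications never reach the DMC.** The committee sentence is ambiguous rather than exclusive. Adverse event forms and complication records still capture these events, and the DMC's role covers safety and interim data. At worst, an event might arrive without the SAE label.
- **A reader might infer a bias between arms,** because the surgical list holds potentially major events and the conservative list only minor ones. The lists follow the different risks described in section 3.8.2, and the protocol states no comparison of SAE rates by arm. Section 4.2 concerns recruitment and the patient-reported outcomes.
- **A reader might put the error at 11 percentage points,** as one missed event in nine operations (1/9). That presumes that an event occurs and is then missed. It is not an expected effect.
- **A reader might call the osteonecrosis entries a flat contradiction.** Section 3.8.2 also gives a mechanism and treats it as a recognised, very small risk, and a rare but foreseeable event can be listed as expected. The two statements are in tension.

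It is also true that this is a pilot meant to estimate recruitment, and the defect does not touch that estimate. But section 2.2 says that the pilot is to test the processes of a full trial, so a faulty definition could carry forward.

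**Conclusion.** The point holds in a limited form. The SAE definition is wrong as written, because it contradicts three later provisions of its own section. Applied literally, it removes serious events on the expected lists from the 24-hour report and moves the expectedness decision from the CI to the site. Whether expected SAEs go to the TSC and DMC is unclear. The osteonecrosis listing needs reconciling with section 3.8.2.

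Complications that are not serious, and serious events that are unexpected, are classified the same way with or without the word. In numbers the exposure is small: roughly a 9–17% chance of any complication among about nine operations, assuming 30% recruitment and the protocol's own complication rate. The case for correction rests on participant safety and on a rule that sites cannot follow consistently.

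**What to change.** In section 3.8.1:

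1. Delete *and unexpected* from the SAE definition, so that seriousness alone defines an SAE.
2. State that expectedness, as confirmed by the CI, is used only to decide REC notification.
3. State that every SAE, expected or not, is reported to the trials unit within 24 hours and to the TSC and DMC, and replace the ambiguous opening of the committee sentence accordingly.
4. Reconcile the listing of osteonecrosis as expected and exempt from REC notification with the statement in section 3.8.2 that no case has been reported.

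The cost is protocol wording, matching guidance on the case report form and a small extra reporting workload. Sample size, outcomes and analysis are unchanged.

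### The surgical exemption from ethics committee reporting (3.8.1) is defined by event type with no limit on severity or outcome, so a related fatal or disabling listed event need not be notified

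*Protocol*

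**What the plan says.** Protocol section 3.8.1 lists the seriousness criteria. The first is "Results in death"; threat to life is the second and lasting or significant disability the fourth. Every SAE is sent to the trials unit within 24 hours, and the CI then confirms causality and expectedness.

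The trigger for the REC is narrower: "SAEs that are deemed to be unexpected and related to the trial will be notified to the Research Ethics Committee (REC) within 15 days".

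The section then sets out two exempt lists.

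- **Surgery.** The list opens with "SAEs that may be expected as part of the surgical interventions, and that do not need to be reported to the main REC are". Its entries are "complications of anaesthesia or surgery (wound infection, bleeding or damage to adjacent structures such as nerves, tendons and blood vessels", followed by "delayed wound healing, and thromboembolic events, hip fracture, osteonecrosis and traction related neuropathies".
- **Conservative care.** The exempt entries are "transient increase in pain, delayed onset muscle soreness or mild bleeding at injection or acupuncture needle sites".

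Section 3.8.2 describes the risks of surgery. Under bleeding it mentions only bruising or a localised haematoma.

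**The concern.** Whether an adverse event is expected normally depends on its nature and also on its severity and outcome. A wound haematoma and a fatal haemorrhage are both bleeding, but only the first is what a committee would understand by an expected complication of an elective arthroscopy. The surgical list in 3.8.1 uses nature alone. Nothing in it separates a minor listed event from one that kills or disables, and the CI is given no criterion for making that separation.

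At stake is prompt notice to the REC. The listed events most likely to alter its view of the trial's safety are the severe ones, and the text leaves their notification to unguided judgement.

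**Working it through.** No sample size, power or event-rate figure enters this point, so there is no arithmetic to reproduce. The check applies the rule as written and compares the relevant texts.

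**Step 1. Apply the rule.** Take a related fatal thromboembolic event after trial surgery.

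1. It is serious under criterion 1 of 3.8.1.
2. Its type is named in the surgical list.
3. The list says events of that type may be expected and need not go to the REC.
4. The 15-day trigger requires an event to be both unexpected and related. If the CI follows the list, the first condition fails and no notification is due.

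The same steps apply to an anaesthetic death or a fatal bleed (criterion 1), a life-threatening bleed (criterion 2) and a permanent nerve injury (criterion 4). No other section requires a listed event with one of these outcomes to go to the REC.

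**Step 2. Compare the two exempt lists.**

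| | Surgery (3.8.1) | Conservative care (3.8.1) |
|---|---|---|
| Bleeding | listed, no limit | needle or injection site only, and mild |
| Pain or soreness | not listed | pain increase must be transient; muscle soreness has no qualifier but is minor by nature |
| Nerve or vessel damage, thromboembolism, anaesthesia | listed, no limit | not applicable |
| Carve-out for fatal or disabling outcome | none | none, and hardly needed |

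Two of the three conservative-care entries have a severity limit. None of the surgical entries does.

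**Step 3. Compare the surgical list with the risks described in 3.8.2.** Bleeding is presented there as bruising or a localised haematoma, whereas 3.8.1 exempts bleeding of any degree. Section 3.8.2 does not mention thromboembolism or death. Its list is introduced as illustrative, and it does mention serious complications such as fracture and deep infection, so silence alone proves little. For bleeding, however, the exemption is plainly wider than the risk described.

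**Step 4. Check whether a neighbouring correction would remove the problem.** The SAE definition itself requires an "untoward and unexpected medical occurrence that" meets one of the criteria, which sits badly with a list of expected SAEs. Deleting the word for unexpected from that definition would settle that conflict. A fatal event of a listed type would still be exempt, because the gap concerns outcome and not the definition.

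**The case against.** The strongest reply is that the exemption is not automatic. Listed events only may be expected, and the CI confirms expectedness for the SAEs received. A CI who judged a fatal embolism unexpected would trigger the 15-day report. This stands, and it limits the finding: the text allows non-notification but does not impose it. It does not remove the finding, because the only guidance given to the CI is a list saying that such events need not be reported.

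A second reply is that other oversight continues. SAEs reach the trials unit within 24 hours, adverse events are recorded on case report forms, complications are collected at 6 weeks and at 3, 6 and 12 months (Table 2), and section 5.1 gives the DMC a safety remit. This also stands. The gap is in expedited notice to the REC, not in safety oversight generally. One reservation is that the sentence on reporting to the steering committee and DMC follows directly on the one about unexpected, related SAEs, so it is unclear whether listed events are covered by it. The general remit in 5.1 does not depend on that sentence.

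A reader might go further in three ways that the protocol does not support.

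- *That 3.8.1 contradicts 3.8.2 on traction injury.* Section 3.8.2 says "The numbness usually resolves within a few hours or days". The qualifier already admits cases that last longer, so there is no contradiction.
- *That the arms were deliberately given different reporting standards.* The difference in wording largely follows from the kinds of event listed, and nothing in the text shows such an intention.
- *That the full trial would inherit the rule.* The pilot is meant to inform a later trial, but no section carries 3.8.1 forward.

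**Conclusion.** The point holds in a limited form. Section 3.8.1 exempts surgical SAEs from REC reporting by type alone and gives no severity criterion for confirming expectedness. Followed as written, it permits a related fatal, life-threatening or permanently disabling event of a listed type to go without 15-day notification. It does not require that outcome, and internal reporting is unaffected.

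The size cannot be put as a probability. A reader might reach for the 1-2% complication risk in 3.8.2 and multiply it up over the expected operations. That would measure the wrong thing: the figure is for any complication, including bruising and passing numbness, and the protocol gives no rate for fatal or disabling events. The number of operations would also have to be assumed. The case therefore rests on the consequence of a single event and not on frequency.

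The recruitment estimate, which is the pilot's purpose, and the planned analyses are not affected. The conclusion assumes that no other approved document outside the protocol already sets a severity limit on the list.

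**What to change.** Add to section 3.8.1, after both exempt lists: *The exemption does not apply to a listed event that is fatal, life-threatening or leaves lasting or significant disability. Such an event is treated as unexpected in severity and, if related, is notified to the REC within 15 days. This holds in both arms.*

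This gives the CI an explicit criterion and reconciles the exempt lists with the seriousness criteria in the same section. In the conservative-care arm it will have almost no practical effect. It changes reporting only and leaves treatment as it is. The cost is a short protocol amendment and, rarely, one additional expedited report.

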3.8.2 Risks and benefits

Both interventions are thought to provide benefit in patients with FAI. There is thought to be a longterm risk of osteoarthritis in patients with FAI. It is not known whether conservative care or arthroscopic surgery have an effect on this risk. The short-term risks of this study relate to the two interventions. These risks are described below:

Operative

Hip arthroscopy requires a general anaesthetic. The risk of complications from hip arthroscopy is about 1-2%⁶⁰. These include:

- Infection – thought to be less than 1 in 1000. If the infection occurred deep within the joint it may require more procedures to wash out the hip joint.
- Bleeding – possibly causing bruising or a local haematoma.
- Traction related – to allow the small arthroscopy instruments into the hip joint, traction is required to separate the hip joint surfaces. Sometimes after the procedure the pressure from the traction can cause some numbness in the groin, leg or foot. The numbness usually resolves within a few hours or days.
- Osteonecrosis – during surgery the blood supply to the hip joint could be damaged. However, there are no reported cases of osteonecrosis following arthroscopic hip impingement surgery so this is a very small risk.
- Femoral neck fractures - This is also a very rare complication. This complication would require a further procedure to fix the fracture.

Non-operative

There are some small risks with pain medications and joint injection. However, the main risk is muscle soreness and transient increases in pain from the exercises that will be undertaken.

3.9 End of trial

The pilot study will be complete when we have approached 60 patients to seek consent for randomisation or when it has become apparent that it is not feasible within 18 months. All patients who are randomised will be followed up for 1 year.

4. Data Management

4.1 Case Report Forms

The Case Report Forms will be designed by the trial coordinator in conjunction with the trial management team. All electronic patient-identifiable information will be held on a secure, password-protected database accessible only to essential personnel. Paper forms with patient-identifiable information will be held in secure, locked filing cabinets within a restricted area of Warwick Medical School. Patients will be identified by a code number only. Direct access to source data/documents will be required for trial-related monitoring. All paper and electronic data will be retained for at least five years after completion of the trial.

4.2 Statistical Analysis

The pilot study is not designed or powered to assess the size of any treatment effect, rather to estimate recruitment rate. The recruitment rate will be estimated based on data collected and a 95% confidence interval determined for this estimate. Treatment differences will be estimated for the primary outcome measure (NAHS) and all secondary outcome measures (IHOT-33, SF-36 and EQ-5D) at 3, 6 and 12 months. In addition to treatment differences the variability (standard deviation) of the outcome measures will be estimated in the target population. Together with the estimated treatment differences, the variability and recruitment rate will be used in power analysis to develop a range of potential trial designs, with recommendations as to which the most feasible option.

In addition to power analysis, summary data measures (e.g. means, medians and standard deviations) will be presented for all outcome measures at each occasion and inferences will be made on temporal changes and any potentially interesting effects within subgroups identified for future work. Analysis will be undertaken in SPSS® and R (<http://www.r-project.org/>) as appropriate.

It seems likely that some data may not be available due to voluntary withdrawal of patients, lack of completion of individual data items or general loss to follow-up. Where possible the reasons for data 'missingness' will be ascertained and reported. Although missing data is not expected to be a problem for this study, the nature and pattern of the missing data will be carefully considered — including in particular whether data can be treated as missing completely at random (MCAR). If judged appropriate, missing data will be imputed, using the multiple imputation facilities available in R (<http://www.r-project.org/>). The resulting imputed datasets will be analyzed and reported, together with appropriate sensitivity analyses. Any imputation methods used for scores and other derived variables will be carefully considered and justified. Reasons for ineligibility, non-compliance, withdrawal or other protocol violations will be stated and any patterns summarized. More formal analysis, for example using logistic regression with 'protocol violation' as a response, may also be appropriate and aid interpretation.

5. Trial Oversight

The day-to-day management of the trial will be the responsibility of the Trial Coordinator, based at Warwick CTU and supported by the CTU administrative staff. This will be overseen by the Trial Management Group, who will meet monthly to assess progress. It will be the responsibility of the Trial coordinator and the clinical research fellow to undertake training of the research associates at each of the trial centres. The trial statistician and health economist will be closely involved in setting up data capture systems, design of databases and clinical reporting forms. A Trial Steering Committee (TSC) and a Data Monitoring Committee (DMC) will be set up.

